## 12.0 Data Management

- Analysis: The primary analysis will be a repeated measures ANOVA for each outcome. The primary independent variables are group (treatment vs. control), evaluation time (baseline and 1-4 weeks of using the device for the primary analysis; follow-up will be included in subsequent analysis), and their interaction. We will also include sex as an independent variable along with its interactions.

- Sample size justification: For the repeated measures design with a significance level of 0.0125 (adjusted for multiple comparisons), at least 80% power, and 5 primary time points, using a standard deviation of 6.4 s and compound symmetry correlation of 0.92 (observed in the pilot study), a sample size of 17 per group will be adequate to detect a minimum difference (futility level) of 7 s. Adjusting for 15% attrition, 20 per group is planned.
- Confidentiality: All data except for the consent forms and HIPPA forms will be de-identified at the time of data recording. All electronic data will be stored in a password-protected research server that is accessible to study personnel only. The server is backed up every day and maintained 24/7 by IT specialists. All paper data with personally identifiable information including the consent forms and HIPPA forms will be stored in a key-locked cabinet in a key-locked room that is accessible to study personnel only. Other paper data without personally identifiable information including testing sheets documenting testing sequences and notes will also be stored in a cabinet in a key-locked room that is accessible to study personnel only.
- Data sharing: Only de-identified coded data will be reported and/or shared with the public and other investigators in publications, in ClinicalTrials.gov, or via network storage.

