- Neural plasticity assessment: Participants will sit on a chair and rest. A TMS coil will be placed on top of the subject's head. The TMS coil location will be moved around slightly to find the 'hotspot' that stimulates neurons with direct monosynaptic projections to the

alpha motoneurons in the spinal cord for the abductor pollicis brevis (APB) muscle, as seen by the evoked potential in the APB (recorded using electromyogram, EMG) immediately after TMS. To record this MEP from the APB muscle, subjects will have the surface EMG electrodes on the skin on top of the APB muscle belly. Noninvasive electrical nerve stimulation will be applied to the participant's wrist via a surface electrode pair, immediately prior to the TMS. This assessment will take place at each evaluation session and last approximately 30 minutes.

- Clinical Assessment: Subjects' clinical upper extremity function scores will be assessed using conventional clinical assessments used in occupational/physical therapy in which participants will be asked to move the affected hand and arm, grasp objects and perform prescribed tasks (e.g., lifting an object off the table, releasing the object into a bin) as quickly as possible. These tests will be videotaped for scoring. The clinical assessments will take place at each evaluation session and last approximately 30 min.
- Biomechanical hand grip control assessment: Subjects will grip an instrumented object, lift the object off a table against gravity, steadily hold the object at a comfortable reaching distance for 5 s, and then slowly and intentionally release the grip until the instrumented object falls. Subjects will repeat this grip-lift-hold-release task 5 times. The biomechanical assessment will take place at baseline, post, and follow-up evaluation session and last ~15 minutes.
- Wear time assessment: Subjects will fill out a self-reported device use log, indicating the time at which they put on and take off the device every day in their home. They will submit the log to study personnel during the weekly visits.
- In-home upper limb use amount assessment: This assessment entails participants wearing accelerometers on both wrists using standard wrist straps for 3 days at baseline, immediately after one month of wearing TheraBracelet, and at follow-up. Subjects will be instructed to wear the accelerometers during the entire day. The wear time assessment will take place at each evaluation session.

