- Home therapy program: Participants and their caregivers will meet with study staff to identify specific hand/arm tasks to practice at home. The goal of this program will be to increase hand/arm use in activities of daily living. Participants will document their progress on check-off sheets and submit them during their weekly laboratory visits.
- Due to COVID-19, some participants may be assessed over the phone only, and may continue with the home intervention (home exercise and watch) while being monitored via weekly phone calls until they could come to the laboratory for full assessments.

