## 14.0 Withdrawal of Subjects (if applicable)

- Subjects who do not show up on scheduled visits may be withdrawn by the investigator.
- For those who voluntarily withdraw from the research, their data collected up to that point may be used by the investigator.

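### The primary repeated measures ANOVA has no stated analysis set or missing-data method; in its classical form it would drop anyone missing one of five visits and could become a completers' comparison

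*Combined protocol and SAP*

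**What the plan says.** Section 12.0 (Analysis): "The primary analysis will be a repeated measures ANOVA for each outcome". The factors are group, evaluation time (baseline and weeks 1 to 4) and their interaction, and "We will also include sex as an independent variable along with its interactions". No estimation method or covariance model is named.

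Section 12.0 (Sample size justification): "a sample size of 17 per group will be adequate to detect a minimum difference (futility level) of 7 s", then "Adjusting for 15% attrition, 20 per group is planned".

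Section 10.0, on clinical testing: "The clinical assessments will take place at each evaluation session". The TMS assessment follows the same schedule. EEG, biomechanical and accelerometer measures are taken only at baseline, post and follow-up.

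Incomplete records are foreseen in three places:
- the 15% attrition allowance in Section 12.0;
- Section 14.0: "Subjects who do not show up on scheduled visits may be withdrawn by the investigator" and "For those who voluntarily withdraw from the research, their data collected up to that point may be used by the investigator";
- Section 10.0: "Due to COVID-19, some participants may be assessed over the phone only".

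No section defines who is analysed, how missing values are handled, what is assumed about them, or any sensitivity analysis.

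**The concern.** A classical (least-squares) repeated measures ANOVA needs a value at every level of the within-subject factor. Someone with four of the five visits contributes nothing. If the analysis is run that way, the groups compared are those who completed, not those who were randomised. If people doing badly leave more often from one arm, that arm looks better than it should and the false-positive rate exceeds the planned 0.0125. Values already collected in a 40-person trial would also go unused.

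Section 14.0 adds a second opening. It permits the use of voluntary withdrawers' data without requiring it, and it is silent on data from people the investigator withdraws. Whether these data are analysed is therefore unsettled, possibly until after they have been seen.

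**Working it through.** **1. The plan's own figures.** Inputs from Section 12.0: SD 6.4 s, compound symmetry correlation 0.92, difference 7 s, alpha 0.0125, power 80%, five time points.
- SD of a five-visit mean = 6.4 × √((1 + 4 × 0.92)/5) = 6.19 s.
- Two-sided normal approximation: n = 2 × [6.19 × (2.498 + 0.842)/7]² = 17.45, so 18 per group; power at 17 is 0.788. A one-sided t test gives exactly 17 (power 0.822). The plan does not state sidedness. The stated 17 is reproduced closely enough.
- Attrition: 17/0.85 = 20, so 3 of 20 per group are counted as lost. This fits an analysis of completers but does not prove one, because such inflation is routine under any method.

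**2. Size of the bias.** Assumptions: no true effect, 20 per arm, normal data. The people with the worst observed week-2 change miss weeks 3 and 4, and the classical ANOVA drops them.
- SD of a change from baseline = 6.4 × √(2 × 0.08) = 2.56 s.
- Under compound symmetry the week-2 and week-4 changes correlate 0.5, because they share the baseline.
- Expected values of the four largest of 20 standard normal values: 1.867, 1.408, 1.131, 0.921.
- 3 lost against 0: the remaining 17 shift by (1.867 + 1.408 + 1.131)/17 = 0.259 SD. Bias in week-4 change = 0.259 × 2.56 × 0.5 = 0.33 s, and 0.33/7 = 5% of the target.
- 4 lost against 2: 5.327/16 − 3.275/18 = 0.333 − 0.182 = 0.151 SD. Bias = 0.151 × 2.56 × 0.5 = 0.19 s.
- 3 lost from each arm: the shifts cancel.

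**3. False-positive rate of the completers' ANOVA.** Simulation of the 4-df group-by-time test at 1.25%, 20,000 trials per scenario, Monte Carlo SE about 0.1 points. Ranges cover repeated runs.

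| Lost | Rejection | Bias, week-4 change |
|---|---|---|
| none | 1.2–1.3% | none |
| 3 v 0, at random | 1.1–1.3% | none |
| 3 v 3, worst week-2 change | 1.7% | none |
| 4 v 2, worst week-2 change | 2.1–2.2% | 0.2 s |
| 3 v 0, worst week-2 change | 2.6–2.8% | 0.33 s |

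Adding sex and its interactions to the ANOVA moves these rates by less than 0.1 points.

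**4. Group main effect.** Under compound symmetry the covariance of (week 2 − baseline) with the five-visit mean is σ²[(1 + 4ρ) − (1 + 4ρ)]/5 = 0. Selection on change therefore does not bias the group main effect. Simulation agrees: 1.2% rejection and a bias of about 0.01 s for 3 against 0.

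**5. Values unused if incomplete cases are dropped.** For 3 against 0, 6 of 200 values are missing and 9 observed values are dropped: 9/194 = 4.6%. If each post-baseline visit is missed with probability 5% (an assumption; the documents give no rate), the complete fraction is 0.95⁴ = 0.815 and about 29 of 192 observed values (15%) go unused; at 3% and 10% the share is 9% and 29%.

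**6. Mixed model under the same scenarios** (REML, unstructured covariance estimated from the data, no sex terms).
- Loss on observed values: bias at most 0.01 s. Rejection is 1.2–1.5% with Kenward-Roger but 3.4–4.2% with an uncorrected Wald test, which is worse than the ANOVA.
- Loss on the unseen week-4 value: bias is 0.46 s against 0.66 s for completers (3 v 0), and 0.29 s against 0.39 s (4 v 2). There is no clear gain in false-positive rate (2.2% in both cases, against 2.6% and 2.1%).

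**The case against.** Dropping incomplete cases is an inference. The plan does not name an estimation method, and a compound symmetry correlation is equally compatible with a mixed-model fit. That stands, so it would be wrong to say that the plan orders a completers' analysis or that collected values will be discarded in every case.

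The 3 against 0 case is not the plan's expectation. A 15% loss in both arms is 3 against 3, which gives no bias. The case also requires exactly the three worst changers to leave. If dropout depends on week-2 change plus chance (standardised change plus Gumbel noise, an assumption), the figures fall to 1.7% and 0.17 s for 3 against 0, and 1.5% and 0.13 s for 4 against 2. The double-blinding described in Section 10.0 makes one-sided loss less likely. All of this stands, and it is why the harm is called modest.

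The phone-only arrangement lasts until participants can attend for full assessments, so it may mean deferred rather than missed visits. It is only partial support. Section 13.0 has the DSMB review a statistical analysis plan, so rules might exist elsewhere; none is in the combined document, and citing them would settle the point.

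A reader might infer a loss of power. For a 7 s difference in change there is none of consequence: power is 0.9996 with 11 per arm. For the five-visit mean, the quantity that nearly reproduces 17, power would fall from 0.788 at 17 per arm to 0.683 at 20 × 0.85 × 0.95⁴ = 13.8 per arm, but that 5% missed-visit rate is assumed, so no power claim rests on it.

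Finally, the gap could be closed by stating an analysis set and a missing-data rule, and the choice of a mixed model is partly preference. It is recommended because it keeps partial records at almost no cost.

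**Conclusion.** The omission is confirmed: the primary analysis has neither an analysis set nor a missing-data method, while the plan itself anticipates incomplete records. The consequence is conditional on the ANOVA being run in its classical form and applies to the outcomes measured at every session.

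Given that, random loss, or equal loss in both arms, causes no bias. Selective and unequal loss raises the group-by-time false-positive rate from 1.25% to about 2.1% with a bias of about 0.2 s (4 v 2), and to about 2.7% with 0.33 s in a one-sided worst case (3 v 0). The group main effect is untouched by loss driven by change; loss driven by level could bias it, but that was not quantified. These figures assume normal data and the plan's SD and correlation.

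Two stronger readings are not supported. The documents do not show that partial records will be dropped. Nor does the permissive wording of Section 14.0 show that the choice of who is analysed would be made after the data are seen; it only leaves that possible. This is a worthwhile and inexpensive improvement, not a flaw that undermines the trial.

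**What to change.** In Section 12.0, fit the same group, time, interaction and sex terms by a likelihood-based (REML) mixed model for repeated measures:
- include all randomised participants in their assigned group, and every observed visit;
- pre-specify the covariance structure and a fallback, for example unstructured, then compound symmetry if the model does not converge;
- specify the Kenward-Roger correction;
- state that missing data are assumed missing at random, and add one sensitivity analysis that departs from this.

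For TMS outcomes, also say how participants who are not tested because of contraindications are treated; they have no TMS data under any method.

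In Section 14.0, state that data collected before any withdrawal, voluntary or by the investigator, will be used, subject to consent.

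The cost is wording and slightly more analysis work in standard software, with no added participants, visits or procedures. There are downsides. The result relies on missing at random, so bias from unseen values is reduced by roughly a quarter to a third but not removed. Without the small-sample correction the mixed model's false-positive rate would be worse than the ANOVA's. The supporting mixed-model simulations left out the sex terms, so the exact recommended model has not been tested.

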## 10.0 Study Design / Methods

- Study design: The study design is a double-blinded randomized controlled study. Subjects will wear the device for at least 8 hours/day every day during their normal activity for a month, during which they will come to the laboratory for weekly evaluation. Subjects will affix the device to the affected wrist using the unaffected hand, similar to wearing a watch. Follow-up evaluation will occur 3 months after. During this time, subjects will not receive other hand therapy. All subjects will be educated at each visit on the importance of using the paretic hand as much as possible in daily living. The device will deliver vibration (treatment) or no vibration (control) all the time. Double-blinding is possible because the treatment vibration is imperceptible (i.e. subthreshold).
- Schedule: Participation in this study will last approximately 4 months. Subjects will come to the laboratory a total of 6 to 9 times. The baseline (1-2) visit will entail the baseline evaluation followed by an introduction to using the device. Then, weekly visits will be for evaluation after using the device for 1, 2, and 3 weeks. The post evaluation (1-2 visits) will occur after using the device for 4 weeks. The follow-up evaluation (1-2 visits) will occur after they stop using the device for 3 months. The baseline, post, and follow up evaluations may be completed in two visits in an effort to reduce fatigue among participants.
- Evaluation: Multi-modal evaluation will be performed as detailed below.
- MRI: One MRI assessment will be performed at baseline. The scan will be 20 minutes in duration. The MRI assessment is to obtain the individual participant's brain anatomy to facilitate subject-specific localization of brain activity.
- EEG: For the EEG assessment, participants will wear an EEG cap on their head. Gel will be applied to individual EEG electrodes with a blunt syringe that does not penetrate the skin (taking approximately 30 min for this preparation). During the assessment, the participant will rest comfortably in a chair and either rest or grip with the fingers. The EEG assessment will take place at baseline, post, and follow-up evaluation session and last approximately 40 minutes including preparation.

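### The five-visit primary ANOVA does not fit the outcomes measured only at baseline and week 4, and the plan does not say whether group or group-by-time decides

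*Combined protocol and SAP*

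**What the plan says.** Section 12.0 (Analysis) sets one model for all outcomes: "The primary analysis will be a repeated measures ANOVA for each outcome". The terms are given as "The primary independent variables are group (treatment vs. control), evaluation time" and their interaction, with sex and its interactions added. The time factor is "evaluation time (baseline and 1-4 weeks of using the device for the primary analysis"; follow-up is left to a later analysis.

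Section 10.0 sets the measurement schedule:
- EEG: "The EEG assessment will take place at baseline, post, and follow-up evaluation session".
- Grip control: "The biomechanical assessment will take place at baseline, post, and follow-up evaluation session".
- Accelerometry: "for 3 days at baseline, immediately after one month of wearing TheraBracelet, and at follow-up".
- The TMS-based neural plasticity assessment and the clinical assessments take place at every evaluation session, so they cover all five primary visits.

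Section 12.0 (Sample size justification) works "with a significance level of 0.0125 (adjusted for multiple comparisons") and five time points, "using a standard deviation of 6.4 s and compound symmetry correlation of 0.92", and arrives at 17 per group for a 7 s difference.

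**The concern.** Three outcome types supply two of the five levels of the primary time factor. A two-level model can be fitted to them, but the plan does not specify it, and it does not say which test would then carry the result.

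The choice of term matters for every outcome. Baseline is one of the levels of time, so the group main effect compares averages that include a pre-treatment value. Randomisation makes the expected baseline difference zero, so a real effect is diluted. Group-by-time does not have this problem. If both are primary and neither is named as decisive, the same data can be read from a test with very high power or from one with low power.

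**Working it through.** **Inputs from section 12.0:** 17 per arm, SD 6.4 s, compound-symmetry correlation r = 0.92, difference 7 s, level 0.0125. The plan does not give sidedness; two-sided is assumed. Power is by noncentral t or F. Sex terms are left out.

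**1. The plan's own figure.** Take 7 s as the group difference in the mean of five visits.
- SD of the mean = 6.4 × √((1 + 4 × 0.92)/5) = 6.19 s.
- n per group = 2 × [6.19 × (2.498 + 0.842)/7]² = 17.45 by the normal approximation, close to the stated 17.
- Noncentral t needs 20 two-sided or 17 one-sided.
- A week-4-minus-baseline contrast has SD 6.4 × √(2 × 0.08) = 2.56 s and would need only 3 (normal) to 5 (t) per group for 7 s.

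So 17 matches a group main effect and does not match an interaction contrast.

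**2. Five visits, 17 per arm, r = 0.92.** The SE of the main effect is 6.19 × √(2/17) = 2.124 s on 32 df. The profiles in the first two rows are assumptions, with no baseline difference.

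| Meaning of 7 s | Mean over five visits | Main-effect power | Group-by-time power (F, 4 and 128 df) |
|---|---|---|---|
| Full effect from week 1 | 4 × 7/5 = 5.6 s | 50% | >99% |
| Linear build-up to week 4 | (0 + 1.75 + 3.5 + 5.25 + 7)/5 = 3.5 s | 18% | >99% |
| Average over all five visits | 7 s | 74% | depends on the profile |

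**3. Two visits (EEG, grip, accelerometry).** The plan gives no SD, effect or correlation for these. As an illustration, the 7/6.4 = 1.09 SD effect is borrowed from the timed measure, and correlations of 0.3, 0.5 and 0.7 are assumed.
- ANCOVA: SE = 6.4 × √(1 − r²) × √(2/17) × √(1 + 1/30), 31 df.
- Change score (the two-level interaction): SE = 6.4 × √(2(1 − r)) × √(2/17), 32 df.
- Group main effect: difference 7/2 = 3.5 s, SE = 6.4 × √((1 + r)/2) × √(2/17), 32 df.

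At r = 0.5 the SEs are 1.93, 2.20 and 1.90 s.

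| r | ANCOVA | Change score | Group main effect |
|---|---|---|---|
| 0.3 | 73% | 53% | 27% |
| 0.5 | 83% | 70% | 23% |
| 0.7 | 95% | 92% | 20% |
| 0.92 | >99% | >99% | 17% |

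**4. Where ANCOVA stops helping.** Its SE is the smaller one when (1 + r) × 31/30 < 2, that is, r < 0.935. At 0.92 the difference detectable with 80% power is 3.08 s for both methods.

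**The case against.** The schedule gap leaves the weekly outcomes alone. The power figure is in seconds, and section 10.0 describes clinical tasks done at speed at every session, so the powered measure is plausibly a weekly one; TMS is weekly too. That stands: the mismatch affects three outcome types, and the question of the decisive term affects all of them.

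A change-score test is valid under randomisation, and the advantage of ANCOVA here rests on assumed correlations and a borrowed effect size. That also stands, which is why the gain is shown as a range and disappears at 0.92.

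The low main-effect figures depend on reading 7 s as a post-baseline effect. If it is the average over all visits, power is about 74%, and that is the reading under which 17 per group approximately reproduces. This limits the point without removing it, because that average still includes baseline.

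A reader might go further in three ways that the documents do not support:
- *That the three outcomes cannot be analysed, or that 17 per group is wrong.* A two-level model can be fitted, and 17 is close to what one reading gives.
- *That ANCOVA always has at least as much power.* It loses trivially above a correlation of about 0.935.
- *That the type I error rate is inflated or that no primary outcome exists.* The available text neither lists the tests sharing 0.0125 nor names the timed outcome, and 0.05/4 is only an inference. But a passage was removed, sections 4.0 and 11.0 are absent, and references 1 to 3 are not cited in what can be read. A list may sit in text not shown, and error control is not shown to fail.

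Section 13.0 calls this a pilot trial. It nevertheless claims at least 80% power at an adjusted level, so the test behind that claim should be identifiable.

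**Conclusion.** The point holds on two counts. First, the five-visit model does not match the schedule of EEG, grip control and accelerometry, and the two-level version is left unspecified. Second, the plan does not say whether group or group-by-time decides. For a 7 s week-4 effect with the plan's inputs, the choice of term moves power from over 99% to 50% or 18%, depending on the assumed time profile; under the averaged reading of 7 s the main effect has about 74%. For the two-visit outcomes, baseline adjustment raises power over the change score from 53/70/92% to 73/83/95% at assumed correlations of 0.3/0.5/0.7 and an assumed 1.09 SD effect.

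This should be changed, with medium confidence. The definition of the tests sharing 0.0125 and the name of the timed outcome are a secondary note only.

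**What to change.** (a) State that EEG, grip control and accelerometry are analysed by ANCOVA of the week-4 value adjusted for baseline, keeping sex as a covariate in line with section 12.0.

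(b) For TMS and the clinical assessments, keep the weekly longitudinal model. Name group-by-time or a baseline-adjusted group difference as the treatment test, and rule out a group main effect that includes the baseline value.

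(c) Have the sponsor confirm which test the 17 per group was computed for and whether 7 s is a week-4 or an averaged difference. If no list exists elsewhere, add the tests that share 0.0125 and name the timed outcome.

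The cost is SAP wording, with no new data or visits. ANCOVA uses one degree of freedom, brings no gain at a correlation of 0.92 and a trivial loss above about 0.935.

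### The primary repeated measures ANOVA states no covariance structure or sphericity correction; on the weekly outcomes an uncorrected group × time test could reject about 1.3 to 3 times too often

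*Combined protocol and SAP*

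**What the plan says.** The analysis plan is in Section 12.0, Data Management. The Analysis item reads: "The primary analysis will be a repeated measures ANOVA for each outcome". The factors are group, evaluation time and their interaction, with sex and its interactions added. The time levels are "baseline and 1-4 weeks of using the device for the primary analysis; follow-up will be included in subsequent analysis". Nothing there mentions a covariance structure, a check of sphericity, a Greenhouse-Geisser or Huynh-Feldt correction, a multivariate test or a mixed model. Nor does it say which term decides the trial.

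The sample size item in the same section uses "5 primary time points", a "significance level of 0.0125 (adjusted for multiple comparisons"), "at least 80% power", a standard deviation of 6.4 s, a difference of 7 s, and a "compound symmetry correlation of 0.92 (observed in the pilot study"). This is the only place where a covariance structure is named.

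Section 10.0 fixes which outcomes have five primary time points. The clinical and TMS assessments are made at every evaluation session. EEG, grip biomechanics and accelerometry are scheduled at baseline, post and follow-up, so they have two time points in the primary window.

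**The concern.** With baseline as one level of time, the group × time interaction asks whether the two groups change differently from baseline. That is the natural test of both aims. The classical univariate F-test for this term needs sphericity, which compound symmetry guarantees. If visits a week apart correlate more strongly than visits four weeks apart, or if participants recover at different rates, sphericity fails and the uncorrected test rejects too often under the null. Both patterns are plausible in a trial whose theory is gradual recovery through greater hand use.

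At stake is the 0.0125 level, which the plan has already lowered for multiplicity. Inflation at the upper end would carry the real error most of the way back to 0.05. Because the plan is silent, an analyst could also choose between corrected and uncorrected p-values after seeing the data.

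**Working it through.** **Inputs from Section 12.0.** Alpha 0.0125 (taken as two-sided; the sidedness is not stated), power 80%, SD 6.4 s, correlation 0.92 with compound symmetry, 5 time points, difference 7 s, 17 evaluable per group, 15% attrition.

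**Step 1: the plan's own figure.** Take the group difference averaged over five visits.

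- SD of a participant's mean = 6.4 × √((1 + 4 × 0.92)/5) = 6.19 s.
- n per group = 2 × 6.19² × (2.498 + 0.842)² / 7² = 17.45, which rounds up to 18. Power at 17 is 78.8%.
- Attrition: 17 / 0.85 = 20 per group.

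The stated 17 and 20 are reproduced to within one participant. The contrast that reproduces them is the visit-averaged group difference, not group × time. A change score with the same inputs would need only 3 per group.

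**Step 2: the test at issue.** With N = 34 participants and 5 times, the uncorrected F for group × time has 4 and 4 × (34 − 2) = 128 degrees of freedom. Departure from sphericity is measured by ε = tr(A)² / (4 tr(A²)), where A is the covariance matrix of four orthonormal time contrasts. ε = 1 means sphericity holds. The Greenhouse-Geisser correction multiplies both degrees of freedom by the estimated ε. At ε = 0.566, for example, they become 4 × 0.566 = 2.26 and 128 × 0.566 = 72.4.

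**Step 3: error under the null.** Simulation with normal data, 17 per group, nominal 0.0125, no missing data and no sex term. There were 100,000 trials per row, except 40,000 for the slope rows. Every covariance pattern other than the first is an assumption.

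| Covariance | ε | Uncorrected | × nominal | Greenhouse-Geisser |
|---|---|---|---|---|
| Compound symmetry 0.92 | 1.00 | 1.2% | 1.0 | about 1.0% |
| Stable participant effect + AR(1) 0.3, mean correlation 0.92 | 0.92 | 1.6% | 1.3 | 1.1% |
| Same, AR(1) 0.5 | 0.81 | 2.1% | 1.7 | 1.2% |
| Same, AR(1) 0.7 | 0.69 | 2.7% | 2.2 | 1.3% |
| Same, AR(1) 0.9 | 0.58 | 3.6% | 2.8 | 1.5% |
| Pure AR(1) 0.92 | 0.57 | 3.5% | 2.8 | 1.5% |
| Pure AR(1) 0.959, mean correlation 0.92 | 0.55 | 3.8% | 3.0 | 1.5% |
| Compound symmetry + slopes, SD 0.6 s/week | 0.88 | 1.7% | 1.4 | 1.0% |
| Same, SD 1.2 s/week | 0.55 | 3.8% | 3.0 | 1.6% |

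The Monte Carlo standard error is about 0.04 to 0.06 percentage points for the 100,000-trial rows, and up to about 0.1 for the slope rows, so the single 1.6% is not distinguishable from 1.5%. Results with 20 per group are nearly the same. At nominal 0.05, the serial-correlation patterns give 1.1 to 1.7 times nominal.

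**Step 4: which outcomes are exposed.** With two time levels there is only one time contrast, so sphericity cannot fail. That removes EEG, grip biomechanics and accelerometry in the primary window and leaves the clinical and TMS outcomes. The group test averaged over visits uses one number per participant and does not depend on sphericity.

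**The case against.** A reader might infer that the analysis rests on compound symmetry and that its error is therefore about three times nominal. The documents support neither statement. Compound symmetry is a sizing input only; the Analysis item neither adopts nor excludes a structure or a correction, and a repeated measures ANOVA is often reported with Greenhouse-Geisser. The protocol also says that the 0.92 was observed in the pilot. If compound symmetry holds, there is no inflation. Threefold inflation needs nearly pure serial decay at 0.92 to 0.96, or slopes so variable (SD 1.2 s/week) that the mean correlation falls to 0.87 and the baseline to week 4 correlation to 0.74, below the plan's own 0.92. All of this stands, and it turns a single figure into a range that depends on assumptions.

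It does not remove the point. One correlation, reported without visit-level values, pilot size or precision, cannot show that correlation is constant over time. Moderate serial correlation around a stable participant effect keeps the mean at exactly 0.92 and still gives 1.3 to 2.2 times nominal.

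It is also fair that the plan names no deciding term and that the visit-averaged test, which matches the sizing, is unaffected. But that average includes baseline, before any treatment, so it is a weak test of treatment. Finally, a mixed model on weeks 1 to 4 changes the contrast as well as the covariance. That is true; the Greenhouse-Geisser sentence alone is enough to answer the error-rate problem.

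**Conclusion.** The point holds for the clinical and TMS outcomes, conditionally. As written, the plan permits an uncorrected group × time test whose error at nominal 0.0125 is correct under compound symmetry and about 1.6% to 3.8% under the decay and slope patterns examined. The size depends on assumed patterns, because the documents contain no visit-level correlations. It also depends on the classical univariate F-test being run without correction, and on group × time being the deciding term, which is the natural reading but is not stated. The documents do not show that the trial's test is invalid, only that its validity has been left to an unstated assumption.

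**What to change.** Either of two changes to Section 12.0 settles it.

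1. Keep the ANOVA. Name group × time as the deciding term, and state that all time and group × time tests on outcomes measured at all five visits use the Greenhouse-Geisser correction.
2. Preferably, replace it for those outcomes with a mixed model for repeated measures on weeks 1 to 4: baseline as covariate, treatment × week, unstructured covariance and Kenward-Roger degrees of freedom. With baseline moved out of the time factor, the interaction no longer picks up a difference that is constant from week 1, so the text must also name the treatment contrast that decides. This model keeps participants who miss a visit, which matters given the planned 15% attrition and the provision in Section 10.0 for phone-only assessment during COVID-19.

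The cost is analysis-plan wording, plus a slight loss of degrees of freedom if compound symmetry truly holds: the corrected test then runs at about 1.0% instead of 1.25%. No visit, measurement or sample size has to change.
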